7.22 Definition of Dose-Limiting Adverse Events

Dose Limiting Adverse Events:

Dose Limiting Toxicity (DLT) will be defined as any of the following events that is determined to be possibly, probably, or definitely related to lenalidomide (as determined by the investigator) within the first cycle of therapy irrespective of whether the adverse events resolved:

- Grade 3 or higher neutropenia with fever $\geq 38.5^{\circ}\text{C}$
- Grade 4 neutropenia ≥ 7 days
- Grade 4 or higher thrombocytopenia
- Other non-hematologic Grade 4 or higher adverse event not present prior to starting therapy or not due to underlying cause

Management and dose modifications associated with the above AEs are outlined in Section 8.0.

7.23 Dose Escalation Phase:

A standard cohort of 3 phase I design will be used where subjects will be initially enrolled in groups of three and individually assessed for safety and DLT. For a subject to be considered evaluable for dose limiting toxicity the subject must have received at least one dose of both drugs in Cycle 1 and have not been withdrawn from the study prior to Cycle 2 secondary to a drug related AE. If a subject withdraws from the study without meeting these criteria for reasons other than adverse events, the subject will be replaced in that cohort.

Doses will be escalated until the first observation of a DLT as defined in Section 7.22 in the first treatment cycle in a group of at least 3 subjects treated at that dose level. All DLTs occurring in the first 3 cycles of the Phase I and II components will be collected and considered in the overall analysis, however, only DLTs occurring in Cycle 1 will define MTD during the Phase I component. Severity grading will be defined using National Cancer Institute Common Terminology Criteria for Adverse Events (NCI CTCAE V4.0). A one-time dose escalation of lenalidomide after 2 cycles of treatment due to improvement of renal function is allowed within an individual patient as described in Section 8.3.

A standard 3+3 phase I design will be used to determine the recommended dose in each renal dysfunction group. Dose level 1 will be the initial dose level (see Tables in Section 7.21).

- For current dose level accrue 3 patients (accrual for the group [Group A, B, or C] will be temporarily closed while the 3 patients are evaluated for DLT).
- If exactly 0/3 experience a DLT, then proceed to the next higher dose level.

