- If exactly 1/3 experience a DLT, then accrue 3 more patients at the current dose level (accrual for the group [Group A, B, or C] will be temporarily closed while the 3 additional patients are evaluated for DLT). If (out of 6 patients) there are at least 2 that experienced a DLT, the recommended dose level has been exceeded. Drop down one dose level.
- If 2 or more (out of 3) patients experience a DLT, the recommended dose level has been exceeded. Drop down one dose level.

The recommended dose level for the phase II portion of the trial is the maximum dose level that resulted in less than 2/6 patients with DLTs. Patients who experience DLTs will be dose reduced to the next lower dose level.

Dose escalation will proceed within each group [Group A, B, or C] according to the following scheme. A DLT is defined above.

Number of Patients with DLT at a Given Dose Level	Phase I Escalation Decision Rule
0 out of 3	Enter 3 patients at the next dose level.
≥ 2	Dose escalation will be stopped. This dose level will be declared the maximally administered dose (highest dose administered). Three (3) additional patients will be entered at the next lowest dose level if only 3 patients were treated previously at that dose.
1 out of 3	Enter at least 3 more patients at this dose level. 
 • If 0 of these 3 patients experience DLT, proceed to the next dose level. • If 1 or more of this group suffer DLT, then dose escalation is stopped, and this dose is declared the maximally administered dose. Three (3) additional patients will be entered at the next lowest dose level if only 3 patients were treated previously at that dose.
≤ 1 out of 6 at highest dose level below the maximally administered dose	This is generally the recommended phase 2 dose. At least 6 patients must be entered at the recommended phase 2 dose.

Once the MTD is reached in the Phase I component for Group A, B or C, the group with the defined MTD dose will immediately be eligible to go to the Phase II component, and will not have to wait for the MTD in the other two groups

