8.3 Lenalidomide Dose Modification Based On Non-Hematological Toxicity (see Table 8.31)

A one-time dose escalation in lenalidomide of one dose level is allowed at any one time point after completion of 2 cycles of treatment if one of the following conditions is met:

1. The patient was originally registered in Group C but has renal function improvement to a point that dialysis is no longer needed; or
2. The patient was originally registered in Group B but has renal function improvement to $\geq 30 \text{ CrCl (mL/min)}$.

All previously established or new toxicities observed any time, are to be managed as per Table 8.31 and Table 8.4.

If drug must be discontinued, the patient comes off treatment and goes to follow-up per Section 4.0 and event monitoring per eCRF completion guidelines. If the toxicity resolves and drug is to be restarted, the dose must be reduced by dose levels as indicated in the dose reduction table.

Please note: Held doses are not made up.

Table 8.31: Dose Modification for Lenalidomide

NCI CTC Toxicity Grade	Day 2-14 of Cycle	≥Day 15 of Cycle
Grade 3 neutropenia associated with fever (temperature $\geq 38.5^{\circ}\text{C}$) or Grade 4 neutropenia	
 Hold lenalidomide. Follow CBC weekly. If neutropenia has resolved to \leqgrade 2, restart at next lower dose level and continue the cycle until day 21. 	
 Hold lenalidomide for remainder of cycle. Restart lenalidomide next cycle (decrease dose by one dose level).
Thrombocytopenia \geq Grade 3 (platelet count $< 50,000/\text{mm}^3$)	
 Hold lenalidomide. Follow CBC weekly. If thrombocytopenia resolves to \leqgrade 2, restart lenalidomide at next lower dose level and continue the cycle through Day 21. 	
 Hold lenalidomide for remainder of cycle. Restart lenalidomide next cycle (decrease dose by one dose level).
Non-blistering rash Grade 3	
 If Grade 3, hold lenalidomide dose. Follow weekly. If the adverse event resolves to \leqgrade 1, restart lenalidomide at next lower dose level and continue the cycle through Day 21. 	
 Hold lenalidomide for remainder of cycle. Restart lenalidomide next cycle (decrease dose by one dose level).

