Grade 4	
 Discontinue lenalidomide study drug and go to follow-up and event monitoring. 	
 Discontinue lenalidomide study drug and go to follow-up and event monitoring.
Desquamating (blistering) rash- any Grade	
 Discontinue lenalidomide study drug and go to follow-up and event monitoring. 	
 Discontinue lenalidomide study drug and go to follow-up and event monitoring.
Erythema multiforme \geq Grade 3	
 Discontinue lenalidomide study drug and go to follow-up and event monitoring. 	
 Discontinue lenalidomide study drug and go to follow-up and event monitoring.
Sinus bradycardia/other cardiac arrhythmia Grade 2 \geq Grade 3	
 Hold lenalidomide dose. Follow at least weekly. If the adverse event resolves to \leqgrade 1, restart lenalidomide at next lower dose level and continue the cycle through Day 21. 	
 Hold lenalidomide for remainder of cycle. Restart lenalidomide next cycle (decrease dose by one dose level).
	
 Discontinue lenalidomide study drug and go to follow-up and event monitoring. 	
 Discontinue lenalidomide study drug and go to follow-up and event monitoring.

Allergic reaction or hypersensitivity Grade 2-3	
 Hold lenalidomide dose. Follow at least weekly. If the adverse event resolves to \leqgrade 1, restart lenalidomide at next lower dose level and continue the cycle through Day 21. 	
 Hold lenalidomide for remainder of cycle. Restart lenalidomide next cycle (decrease dose by one dose level).
Grade 4	
 Discontinue lenalidomide study drug and go to follow-up and event monitoring. 	
 Discontinue lenalidomide study drug and go to follow-up and event monitoring.
Venous thrombosis/embolism \geq Grade 3	
 Hold lenalidomide and start therapeutic anticoagulation; restart lenalidomide at investigator's discretion (maintain dose level). 	
 Hold lenalidomide for remainder of cycle. See Anticoagulation Consideration (see Section 9.4). Restart lenalidomide next cycle (decrease dose by one dose level).

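### Protocol 7.23 orders a dose reduction for every patient with a DLT, while Table 8.31 takes patients with five kinds of grade 4 DLT off lenalidomide

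*Protocol*

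**What the plan says.** Section 7.22 of the protocol defines a DLT as one of four kinds of event in cycle 1, at least possibly related to lenalidomide, whether or not it resolves. The non-hematologic kind is "Other non-hematologic Grade 4 or higher adverse event not present prior to starting therapy or not due to underlying cause". The section closes with a pointer: "Management and dose modifications associated with the above AEs are outlined in Section 8.0".

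Section 7.23 follows, sets out the 3+3 rule, and adds for the individual patient: "Patients who experience DLTs will be dose reduced to the next lower dose level". That sentence contains no exception, no condition that the drug be restarted, and no reference to Section 8.0.

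Section 8.3 governs management after toxicity: "All previously established or new toxicities observed any time, are to be managed as per Table 8.31 and Table 8.4". It has two branches. In the first, "If drug must be discontinued, the patient comes off treatment and goes to follow-up". In the second, "If the toxicity resolves and drug is to be restarted, the dose must be reduced by dose levels", and the sentence goes on to tie the reduction to what the dose reduction table indicates. For several events the action in Table 8.31, in both day columns, is "Discontinue lenalidomide study drug and go to follow-up and event monitoring".

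**The concern.** A patient with, say, a related grade 4 allergic reaction in cycle 1 of Phase I falls under both rules. Section 7.23 says to continue one level lower; Table 8.31 says to stop. A site that took 7.23 literally would give lenalidomide again to a patient whom the table removes from it.

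The protocol itself treats such reactions as reasons to withhold the drug. Exclusion criteria 3.25 and 3.26 bar patients with known hypersensitivity to this drug class or a history of Stevens-Johnson syndrome on similar drugs. Section 15.16 lists Stevens-Johnson syndrome, toxic epidermal necrolysis, angioedema and anaphylaxis among rare events reported with lenalidomide. What is at stake is a safety instruction in the dose-escalation phase, not an inference.

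**Working it through.** No stated figure depends on the disputed sentence, so the check is a comparison of texts. Table 8.31 has 13 event-and-grade entries. The line labelled grade 4 that follows the grade 3 non-blistering rash entry is read as part of that rash row, because the table is broken across pages in the text available.

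**Step 1. Which entries can contain a DLT?** Three are limited to grades below 4 and are non-hematologic, so they cannot: rash grade 3, arrhythmia grade 2, allergic reaction grade 2-3. That leaves 13 - 3 = 10, of which 2 are hematologic and 8 are not.

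**Step 2. Compare the actions for an event that is a DLT.**

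| Table 8.31 entry | Table 8.31 action | Agrees with 7.23? |
|---|---|---|
| Neutropenia (grade 3 with fever, or grade 4) | Hold, restart one level lower | Yes |
| Thrombocytopenia, grade 3 or higher | Hold, restart one level lower | Yes |
| Non-blistering rash, grade 4 | Discontinue | No |
| Blistering rash, any grade | Discontinue | No |
| Erythema multiforme, grade 3 or higher | Discontinue | No |
| Arrhythmia, grade 3 or higher | Discontinue | No |
| Allergic reaction, grade 4 | Discontinue | No |
| Venous thrombosis/embolism, grade 3 or higher | Days 2-14: restart at same dose; from day 15: one level lower | Not on days 2-14 |
| Thyroid dysfunction, grade 3 or higher | Hold, restart one level lower | Yes |
| Other related non-hematologic, grade 3 or higher | Hold, restart one level lower | Yes |

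Non-hematologic tally: 5 discontinue + 1 keeps the dose on days 2-14 + 2 agree = 8. For blistering rash, erythema multiforme and arrhythmia, the table also discontinues below grade 4. Those lower-grade events are not DLTs and create no conflict.

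**Step 3. Which text is in error?** The pointer in 7.22 and the all-toxicities sentence in 8.3 both lead to Section 8.0 or Table 8.31, and 8.3 provides a separate branch for discontinuation. The one-level reduction in the opening text of Section 8.0 concerns patients who resume drug after recovery, so it is consistent with the table. Only the 7.23 sentence is out of line.

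**Step 4. Does any design figure move?** The escalation rule counts DLTs; it does not use what happens to the patient afterwards. With true DLT rate p, the 3+3 probability of escalation is (1-p)^3 + 3p(1-p)^5. At p = 0.1, 0.2, 0.3, 0.4 and 0.5 this gives 0.906, 0.709, 0.494, 0.309 and 0.172, which reproduces the Section 16.14 table (0.91, 0.71, 0.49, 0.31, 0.17). The post-DLT dose does not enter the formula.

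**The case against.** The best defence is that the documents already settle the matter. Section 7.22 ends, just before 7.23, by sending management of these same events to Section 8.0. Section 8.3 applies Table 8.31 to every toxicity at any time. Nor can the 7.23 sentence be carried out alone: it gives no hold rule, recovery threshold or restart day, and for a patient at dose level 1 the next lower level appears only in Tables 8.11 to 8.13. A site has to open Section 8 to act, and there it meets the instruction to discontinue.

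Most of this stands. It shows that the table is intended to govern and that actual re-exposure is unlikely. It does not remove the contradiction. The 7.23 sentence comes after the pointer, speaks specifically of DLT patients and is unqualified, so it could be read as the special Phase I rule. No clause says which text takes precedence.

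A reader might also infer that the venous thrombosis cell is an error in Table 8.31, because its days 2-14 action, at the investigator's "discretion (maintain dose level"), seems to clash with the restart sentence in 8.3. The documents do not establish that. The restart sentence refers to what the dose reduction table indicates; if that means Table 8.31, keeping the dose is what the table indicates. The cell is specific and tied to therapeutic anticoagulation, and changing it would be a clinical preference. Its one clear conflict is with 7.23, for a related grade 4 event in cycle 1.

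**Conclusion.** The inconsistency is real and confined to one sentence in 7.23. Five of the eight non-hematologic entries that can contain a DLT carry an opposite instruction, and a sixth differs on days 2-14. These are counts of table entries. The documents give no expected frequency for these events at grade 4, so no number of affected patients can be stated.

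The conclusion rests on reading the split rash row as above, and on each event being new, at least possibly related to lenalidomide, and in cycle 1.

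A reader might infer that the conflict reaches the MTD or the Phase II test. It does not: DLT counting, the MTD rule, the sample size, the primary endpoint and the stated error rates are unchanged. Nor do the documents support a claim that sites are likely to re-treat these patients. The correction is worth making because the instruction concerns safety and costs almost nothing to put right.

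**What to change.** Replace the 7.23 sentence with: *A patient with a DLT will be managed per Section 8.0 and Table 8.31 (lenalidomide dose reduced, maintained or discontinued as specified there).* Including the word *maintained* also resolves the conflict between 7.23 and the venous thrombosis cell. No edit is needed to Table 8.31, to the restart sentence in 8.3 or to the opening of Section 8.0.

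As an optional tidy-up in the same amendment, delete or align the separate 7.23 sentence that has escalation continuing until a first DLT is seen. It departs from the 3+3 rule only when one DLT in three is followed by none in three, and the 3+3 bullets, the decision table and Section 16.14 already override it.

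The cost is one sentence replaced and, if wanted, one deleted or aligned. There are no new data and no change to sample size or analysis.

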8.0 Dosage Modification Based on Adverse Events for Phase I and Phase II

Treatment modifications are based on adverse events. All adverse events should be graded according to the NCI Common Terminology Criteria for Adverse Events Version 4.0 (CTCAE V4.0).

Subjects will be evaluated for AEs at each visit with the NCI CTCAE V4.0 used as a guide for the grading of severity. Refer to Tables below for specific Lenalidomide and Dexamethasone dose reduction steps. Subjects who cannot tolerate lowest dose level are to be discontinued from the treatment phase of the study. Subjects experiencing \geq grade 3 non-hematologic or grade 4 hematologic adverse events will have their study drug held per Table 8.31. Held doses are not made up. Grade 3 or 4 AEs must resolve to \leq grade 2 in severity prior to resumption of study medications. Administration of the next drug dose is to be continued with a one-level dose reduction of the relevant drug as indicated in dose reductions. Once a subject's dose has been reduced, no dose re-escalation is permitted except for a possible one-time dose escalation of lenalidomide in the event of improved renal function as described in Section 8.3.

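### The text of Sections 8.0 and 8.3 requires a lower lenalidomide dose on restart, but the venous thrombosis row of Table 8.31 keeps the dose on Days 2-14; hold and recovery wording also differs

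*Protocol*

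**What the plan says.** Protocol Section 8.0 sets three general rules.

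- Hold: subjects with at least "grade 3 non-hematologic or grade 4 hematologic adverse events will have their study drug held per Table 8.31".
- Recovery: Grade 3 or 4 events must come down to at most "grade 2 in severity prior to resumption of study medications".
- Restart: "Administration of the next drug dose is to be continued with a one-level dose reduction of the relevant drug as indicated in dose reductions". The same paragraph bars later re-escalation, apart from a single increase for improved renal function.

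Section 8.3 sends all toxicities to Table 8.31 and Table 8.4, and then says that if drug is restarted after a toxicity resolves, "the dose must be reduced by dose levels as indicated in the dose reduction table".

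Table 8.31 gives rules by event and by part of the cycle. For venous thrombosis or embolism of Grade 3 or higher on Days 2-14, it says to hold, anticoagulate and "restart lenalidomide at investigator's discretion (maintain dose level"). From Day 15 the same row holds drug for the rest of the cycle and restarts one level lower.

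Section 7.23 says that patients who have a DLT go to the next lower dose level.

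**The concern.** These are operating instructions for sites. A site that works from the text of Section 8.0 or 8.3 would restart lenalidomide one level lower after a Day 2-14 thrombosis. A site that works from the table would restart at the same level. Because a reduction generally cannot be reversed, the choice carries into later cycles.

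Two things are at stake. The first is consistent handling of a serious event that the protocol itself stresses (Section 9.4 makes thrombosis prophylaxis mandatory). The second is the meaning of the dose data: Sections 16.22 and 16.37 summarise dose level and total dose per agent in each cycle, and Section 1.7 plans 10 Phase I and 30 Phase II sites. Divergent readings would add variation that reflects the document and not tolerability.

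**Working it through.** There is no design figure to reproduce. The check sets the current text side by side, leaving the amendment log aside.

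**Restart dose**

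| Source | Event | Dose on restart |
|---|---|---|
| Section 8.0 | Grade 3 or 4 events generally | One level lower |
| Section 8.3 | Any toxicity that resolves, drug restarted | Lower |
| Section 7.23 | Any DLT | Next lower level |
| Table 8.31, thrombosis of Grade 3 or higher, Days 2-14 | That event | Same level |
| Table 8.31, thrombosis of Grade 3 or higher, Day 15 on | That event | One level lower |

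Only the Day 2-14 cell disagrees with the general text. The change of rule at Day 15 within the row is not itself a contradiction. Section 7.23 applies only where the thrombosis is a DLT under Section 7.22: Cycle 1, at least possibly related to lenalidomide, and Grade 4 or higher under the non-hematologic item. A Grade 3 thrombosis is not a DLT.

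Size for one patient: level 2 was open in every group on 3 November 2010. One step down from level 2 (Tables 8.11 to 8.13) changes the lenalidomide dose as follows. The schedule is the same at both levels within each group.

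- Group A: (15 − 10)/15 = 33%
- Group B: (25 − 15)/25 = 40%
- Group C: (10 − 5)/10 = 50%

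Other steps differ. These figures show how far apart the two readings are; they do not say which is right.

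**Hold trigger**

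Table 8.31 holds lenalidomide for four events that Section 8.0's trigger does not name:

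- Grade 3 thrombocytopenia
- "Grade 3 neutropenia associated with fever"
- Grade 2 arrhythmia
- Grade 2 allergic reaction

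**Recovery grade**

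| Event, Days 2-14 | Section 8.0 | Table 8.31 |
|---|---|---|
| Grade 3 non-blistering rash | Grade 2 or less | Grade 1 or less |
| Grade 3 allergic reaction | Grade 2 or less | Grade 1 or less |
| Thrombocytopenia, Grade 3 or 4 | Grade 2 or less | Grade 2 or less |

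Arrhythmia does not belong in this comparison. The table's Grade 1 recovery applies to Grade 2 arrhythmia, Section 8.0's recovery rule covers Grades 3 and 4, and the table discontinues lenalidomide at Grade 3 or higher.

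**How many patients**

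The documents give no thrombosis rate. For thrombocytopenia, Section 1.3 gives Grade 3-4 rates of 13.8% with CrCl below 50 mL/min and 18.8% with CrCl below 30 mL/min. The latter is 3/16 = 18.75%. Grade 4 is held under both passages, so only the Grade 3 share could be affected, and it is not reported. Both percentages are therefore ceilings.

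**The case against.** The strongest reply is that the protocol already names a governing source. Section 8.0 refers to the tables for specific steps and holds drug per Table 8.31, and Section 8.3 says that toxicities are managed per Table 8.31 and Table 8.4. On that view Section 8.0 is a summary. Its hold sentence does not say that drug continues at Grade 3 hematologic toxicity, and its recovery sentence sets a minimum that the stricter rows also meet.

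Much of this stands. The hold and recovery differences can be met together by following the table, so they are loose drafting and not rules that exclude each other. The reply does not settle the restart dose. Section 8.3, having pointed to the table, itself requires reduction on restart. Its reference to the dose reduction table most naturally says by how much to reduce, not whether. Keeping the dose and reducing it cannot both be done.

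A reader might also infer that thrombocytopenia is handled differently throughout and that about 1 patient in 5 to 7 is affected. The documents do not support this. For thrombocytopenia only the hold threshold differs; recovery and the one-level reduction agree, and Section 8.21 uses the same 50,000/µL cut-off on Day 1. The 1 in 5 to 7 simply inverts the pooled Grade 3-4 rates. Those come from trials of lenalidomide 25 mg with dexamethasone 40 mg on Days 1-4, 9-12 and 17-20, whereas dexamethasone is weekly here.

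**Conclusion.** There is one true contradiction: the restart dose after venous thrombosis or embolism of Grade 3 or higher on Days 2-14, where Table 8.31 disagrees with Sections 8.0 and 8.3, and with Section 7.23 if the event is a Cycle 1 DLT. There are two secondary mismatches: four events missing from Section 8.0's hold trigger, and a looser recovery grade in Section 8.0 for two Grade 3 events.

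For an affected patient at dose level 2, the two readings differ by 33% to 50% of the lenalidomide dose. How many patients that would be cannot be worked out from the documents. The conclusion assumes that the general sentences in Sections 8.0 and 8.3 mean what they say without an unstated exception for the thrombosis row.

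A reader might go further and infer that the mismatch biases the MTD, since holding drug at Grade 3 thrombocytopenia could alter who reaches Grade 4. That is possible but not shown: DLTs are defined separately in Section 7.22, and nothing in the documents indicates that sites disregarded the table. The point is a correction to a safety instruction, not a challenge to the design.

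**What to change.** Reconcile the hold, recovery and restart sentences in Sections 8.0 and 8.3, and the DLT dose sentence in Section 7.23, with Table 8.31. The thrombosis row needs an explicit statement: either it is an exception to the general restart rule, or it follows that rule. State in Section 8.0 which passage governs where text and table differ. While there, correct the reference to Table 8.4, since the tables in Section 8.4 are numbered 8.41 and 8.42. The clinical team decides the content of each rule.

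The cost is a text correction in the next amendment and a clarification memo to sites. Sample size and the planned analyses are unaffected. If thromboses have already occurred, a short listing of the restart dose used for each would show whether practice diverged.
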